4.4. Randomization

There is no randomization in this study.

5. PLANNED ANALYSES

5.1. Interim Analyses

No interim analysis is planned for this study.

5.2. Final Analyses

Final analysis is planned to be conducted after database lock of the study.

The study was terminated by Insmed. At time of study termination only 1 subject was enrolled into the study and treated. Therefore the collected study data will only be listed, there will be no summaries.

The sections below describing the planned statistical analysis, which was planned for the full study population according to study protocol.

5.3. Safety Review Committee Review

All available safety, PK, and PD data from each participant will be evaluated by the SRC prior to the next participant in order to determine the value of proceeding with the study and the TPIP dose for each subsequent participant.

6. ANALYSIS SETS

6.1. Safety Analysis Set

All participants who receive a single dose of TPIP will be considered evaluable for safety and included in the safety population.

A separate safety population for participants of EUT will be determined.

6.2. Pharmacokinetic Analysis Set

All participants who receive a single dose of TPIP and have at least one measurable post-dose plasma TP/TRE concentration will be considered evaluable for PK and included in the PK population.

6.3. Pharmacodynamic Analysis Set

All participants who receive a single dose of TPIP and have a baseline datapoint and at least one measurable post-dose PD datapoint will be considered evaluable for PD and included in the PD population.

6.4. Biomarker Analysis Set

All participants who receive a single dose of TPIP and have at least one measurable post-dose biomarker datapoint will be considered evaluable for biomarkers and included in the biomarker population.

A separate biomarker population for participants of EUT will be determined.

7. GENERAL STATISTICAL CONSIDERATIONS

Due to the limited number of participants in the study and planned dose escalation after each participant, the observed study data will be presented in by-participant listings. By-participant listings will comprise of all observed data, e.g., single-dose inpatient treatment period and EUT. For selected data points, summaries will be provided only for an overall group. If three or more participants have received the same dose of study drug, summary tables will be provided for those dose group(s).

All statistical analyses will be conducted using statistical analysis system SAS® Version 9.4 or higher (SAS Institute, Cary, NC).

Descriptive statistics for continuous variables include n, mean, standard deviation (SD), median, minimum, maximum, 1st quartile and 3rd quartile (if required). Summaries of continuous variables that have some values recorded using approximate values (e.g., < or >) will use the numeric part of the value in calculations. Listings will present the data in its original format.

Categorical variables will be tabulated by counts and by percentage of participants in corresponding categories. Footnotes will specify the basis for the percentages.

Data from unscheduled visits will not be used in summaries, except for the derivation of baseline.

Listings corresponding to all summaries in this section will be provided. Listings will show data from scheduled and unscheduled visits.

7.1. Baseline Definition

Baseline for single-dose inpatient treatment period will be defined as the last non-missing assessment (including repeated and unscheduled assessments) before the first study drug administration, unless otherwise specified.

Baseline for EUT will be defined as the assessment at EUT Day 1 visit.

The start of EUT period is defined as the date of EUT Day 1 visit.

Change from baseline will be calculated as:

• Change from baseline = post baseline value – baseline value.

7.2. Handling of Missing Data

The imputations described in the following sections will be performed after all efforts fail to obtain the data.

All other data will be reported on available values and no imputations will be performed.

7.2.1. Missing Start and Stop Dates for Prior and Concomitant Medication

The rules to categorize medications to 'Prior' or 'Concomitant' are described in Section 8.4.1. Missing or partially missing start or stop dates will be not imputed.

7.2.2. Missing Start and Stop Dates for Adverse Events

The rules to categorize AEs to 'TEAE' or 'non-TEAE' are described in Section 10.2. Missing or partially missing start or stop dates will be not imputed.

7.3. Derived and Transformed Data

7.3.1. Durations

A duration between one date (*date1*) and another later date (*date2*) is calculated using the following formula:

- Duration (days) = date2 date1 + 1
- Duration (weeks) = duration (days) / 7.

7.3.2. Study Day

Study Day is calculated as date of event minus the date of first exposure to study drug plus one (1) if the date of event is on or after the date of first exposure to study drug.

If the date of event is before the date of first exposure to study drug, the Study Day will have negative values and is calculated as (date of event minus the date of first exposure to study drug).

Consequently, there is no Study Day zero (0).

8. STUDY POPULATION SUMMARIES

The safety analysis set will be used for all study population summaries unless otherwise stated.

8.1. Participants Disposition

For participants screened (participants who have signed the informed consent) the following will be summarized for overall (if applicable also by dose group):

- the number of participants who are screened;
- the number of participants who continue into the study (number of participants who are not screen failure);
- the number of participants who failed screening and the reasons for screen failure;
- the number of participants who are treated in single-dose inpatient treatment period;
- the number of participants who completed the study (single-dose inpatient treatment period);
- the number of participants who discontinued treatment and the reason for discontinuation (single-dose inpatient treatment period);
- the number of participants who discontinued from study and the reason for discontinuation (single-dose inpatient treatment period);

- the number of participants in EUT;
- the number of participants who completed the EUT;
- the number of participants who discontinued treatment in EUT and the reason for discontinuation:
- the number of participants who discontinued from EUT and the reason for discontinuation;
- the number of participants in each analysis population.

A separate summary (if applicable) will be provided for subjects screened for EUT.

Participant disposition data will also be presented in a by-participant listing for screened participants.

8.2. Protocol Deviations

A protocol deviation is any change, divergence, or departure from the study design or procedures defined in the protocol. An important deviation (referred to as a major deviation) is a subset of protocol deviations that leads to a participant being discontinued from the study, or significantly affects the participant's rights, safety, or well-being or the completeness, accuracy, and reliability of the study data. An important deviation can include nonadherence to inclusion or exclusion criteria or nonadherence to Food and Drug Administration regulations or International Council for Harmonisation (ICH) E6(R2) guidelines.

Protocol deviations will be documented by the clinical monitor throughout the course of monitoring visits. The investigator will be notified in writing by the monitor of deviations. The Institutional Review Board should be notified of all protocol deviations, if appropriate, in a timely manner.

All protocol deviations will be presented in a by-participant listing, including the categorization of the deviation as major or not.

8.3. Demographics, Baseline Characteristics, Medical History

8.3.1. Demographics

The demographic characteristics consist of age (years), sex, race, and ethnicity. Baseline characteristics were observed in terms of screening weight (kg), height (cm), body mass index (BMI) (kg/m2), body surface area (BSA) (m²), and tobacco use.

Participant demographic and baseline characteristics will be summarized for overall treatment group (if applicable also by dose group) and presented in a by-participant listing.

A separate summary (if applicable) and listing will be provided for safety analysis set of EUT.

8.3.2. Medical History

Medical history will be coded using the Medical Dictionary for Regulatory Activities (MedDRA, Version 25.0).

Medical history will be summarized by system organ class (SOC) and preferred term (PT) for overall treatment group (if applicable also by dose group) and presented in a by-participant listing.

8.4. Medications and Treatments

8.4.1. Prior, Concomitant and Post Medications

Information regarding prior medications taken by the participant within the 30 days before signing the informed consent form (ICF) will be recorded in the participants electronic case report form (eCRF).

Any concomitant medication deemed necessary for the welfare of the participant during the study may be given at the discretion of the investigator. If a concomitant medication is taken, except for those specified in the protocol, a joint decision will be made by the investigator and the sponsor to continue or discontinue the participant based on the time the medication was administered, its pharmacology and PK, and whether the use of the medication will compromise the safety of the participant or the interpretation of the data. The investigator is responsible for ensuring that details regarding the medication are adequately recorded in the eCRF.

Prior, concomitant and post medications will be coded using the latest version of the World Health Organization (WHO) Drug Dictionary (202203).

Concomitant medications are those medications taken on or after the first dose of study drug, i.e., the end date is on or after the date of first study drug dosing (but before 30 days after last dose of study drug) or ongoing. If the end date of a medication is partially missing, and the possible interval for the end date includes the date of first study drug dosing or the date of 30 days after last dose of study drug dosing, the medication is considered 'Concomitant'.

Post medications are those medications taken on or after the date of 30 days after last dose of study drug, i.e., the start date is on or after 30 days of last study drug dosing.

Prior medications are those medications taken before the first dose of study drug. A medication that starts prior to first dose of study drug but continues after the first dose of study drug is classified both in prior and concomitant medications. If the medication continues after the date of 30 days after last study drug dosing, the medication will be also classified as 'Post'. A medication is classified as 'Prior' if the eCRF question 'Started prior to study drug' is answered 'Yes'.

All prior, concomitant and post medications will be summarized for overall treatment group (if applicable also by dose group) and presented in a by-participant listing.

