4. STUDY DESIGN

4.1. Summary of Study Design

This is a Phase 2a, open label study to assess the safety, tolerability, PD effects and PK of TPIP administered to participants with PAH (approximately 6 to 10 evaluable participants are planned for the study). This is the first study of TPIP in participants with PAH. Each participant will receive a single dose of TPIP. The first participant will receive a dose containing 112.5 µg of TP. The TP dose level for each subsequent participant will be determined following review and adjudication of all available safety, PK, and PD data from the previous participant(s) by the safety review committee (SRC) (Section 1.3.2.1 of study protocol).

This is a "proof of mechanism" study designed to investigate the following:

- 1. The safety and tolerability of TPIP in participants with PAH;
- 2. The relationship between the PK and PD effects of TPIP in participants with PAH, and

^b Echocardiogram optional at investigator discretion

^c Pulmonary CT scan optional at investigator discretion

3. The duration of the PD effects of a single dose of TPIP in participants with PAH.

[figure not shown]
The cardiopulmonary and overall functional status of patients with PAH can be labile and medical instability can develop quickly. The study is designed to provide maximal safety and minimal risk to participants. As such, there is considerable flexibility built into the protocol to allow Investigator discretion with the frequency, timing, and/or conduct of PD and PK assessments to ensure participant safety. Because the study requires an overnight inpatient treatment period, Institutional requirements for elective inpatient admissions, which may vary from site to site, will be followed.

For individual participants, the study will consist of an outpatient screening period lasting up to 30 days. The inpatient treatment period will start on Study Day 1 and is expected to last overnight into Study Day 2. Outpatient PK sampling and safety follow-up at 48 (\pm 4) hours post TPIP dose will extend into Study Day 3. A remote safety follow-up visit is scheduled for Study Day 30 (\pm 2 days). The 48 hour PK visit will also include safety assessments including electrocardiogram (ECG), clinical laboratory evaluations, vital signs, physical examination, and adverse event (AE) collection.

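### SAP Section 8.4.1 puts the 30-day upper limit for concomitant medications on the end date and no limit on ongoing drugs, so some drugs taken on treatment lose the label and some started after the window gain it

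*SAP*

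**What the plan says.** All the rules are in SAP Section 8.4.1. Section 7.2.1 refers to that section for the classification and says that missing medication dates are not imputed.

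- **Concomitant, lead definition:** "Concomitant medications are those medications taken on or after the first dose of study drug".
- **Concomitant, working rule:** "the end date is on or after the date of first study drug dosing", with the qualifier "but before 30 days after last dose of study drug) or ongoing".
- **Partial end dates:** a drug is Concomitant if the possible interval for its end date contains the first dosing date or the date 30 days after the last dose.
- **Post, lead definition:** "Post medications are those medications taken on or after the date of 30 days after last dose of study drug".
- **Post, working rule:** "the start date is on or after 30 days of last study drug dosing".
- **Overlap sentence, in the Prior paragraph:** "A medication that starts prior to first dose of study drug but continues after the first dose of study drug is classified both" as prior and as concomitant.
- **Continuation sentence, directly after it:** "If the medication continues after the date of 30 days after last study drug dosing", the drug is also Post.

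The section plans summaries and a by-participant listing of all three classes. Section 5.2 states that the study was terminated with one participant treated and that data will only be listed.

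**The concern.** Whether a drug was concomitant depends on whether its use overlapped the window from first dose to 30 days after last dose. Overlap needs two tests: the drug ended on or after the opening of the window, and it started before the close. The SAP applies the first correctly. It then puts the close of the window on the end date as well, and lets ongoing drugs through with no test of when they started.

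The label therefore turns on when, or whether, a drug was stopped, and not on whether it was taken in the window. At stake is the class shown in the medication listing, and in the medication summaries planned for the full study. Two programmers following the section faithfully could also produce different labels, because the lead definitions and the working rules do not agree.

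**Working it through.** No figure in the plan is at issue, so the check applies the stated rules to dated examples.

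**Inputs.** F is the date of first dose and D is the date of last dose plus 30 days. For a single dose on Study Day 1, F = Day 1 and D = Day 1 + 30 = Day 31.

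**Rules as written**

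- Concomitant (working rule): F ≤ end < D, or ongoing.
- Concomitant (overlap sentence): start < F and use continues after F.
- Post (working rule): start ≥ D.
- Post (continuation sentence): use continues after D. The narrow reading limits this to drugs started before F, which are the subject of the preceding sentence. The general reading covers any drug.

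**Rules after the fix**

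- Concomitant: start < D, and (end ≥ F or ongoing).
- Post: any use on or after D. The table counts an ongoing drug as used on D.

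| Start (Study Day) | Stop (Study Day) | As written, narrow | As written, general | After the fix |
|---|---|---|---|---|
| 2 | 30 | Concomitant | Concomitant | Concomitant |
| 2 | 31 (= D) | none | none | Concomitant, Post |
| 2 | 32 | none | Post | Concomitant, Post |
| 2 | ongoing | Concomitant | Concomitant, Post | Concomitant, Post |
| 31 | ongoing | Concomitant, Post | Concomitant, Post | Post |
| 31 | 32 | Post | Post | Post |
| −10 | 32 | Prior, Concomitant, Post | Prior, Concomitant, Post | Prior, Concomitant, Post |

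The classes depend only on where the dates fall relative to F and D, so the same pattern arises for a participant in extended use treatment (EUT), with a later D.

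**What follows under both readings**

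1. Among drugs started on Day 2, one stopped on Day 30 is Concomitant, one stopped on Day 31 or 32 is not, and one still ongoing is Concomitant again. All were taken on treatment, and all meet the lead definition.
2. A drug started on Day 31 is Concomitant as well as Post while ongoing, and Post only once stopped.
3. A drug started on Day 2 with a complete end date of Day 31 is not Concomitant. If the day of that end date is missing, so that the possible interval contains Day 31, it is Concomitant. Better data removes the label.

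**How often dates reach D**

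- Single-dose period: in Section 4.1, "A remote safety follow-up visit is scheduled for Study Day 30", with a window of ±2 days, so Days 28 to 32. If medication dates are collected up to this visit, a stop date on or after D = Day 31 can be recorded only when the visit falls on Day 31 or 32.
- EUT: the follow-up visit is 30 ± 3 days after Week 16. If the last dose is at Week 16, D is the centre of that window and at most 3 days of it lie beyond D. A taper of the full 2 weeks that the Figure 2 notes allow moves D to 14 + 30 = 44 days after Week 16, past the latest planned visit at 33 days.

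**The case against.** The best defence is that the lead definition governs and the rest is loose drafting: a drug started on Day 2 was plainly taken after first dosing, so a sensible programmer would call it Concomitant. That shows the intent, but the working rule is the part that gets programmed, and it says otherwise. The defence confirms the contradiction without removing it.

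Other objections succeed against stronger readings that a reader might infer:

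- *Every drug started on treatment and stopped at or beyond D has no class.* This is certain only for a stop exactly on D. For later stops the general reading of the continuation sentence gives Post.
- *A drug started before dosing and stopped after D has no settled class.* The end-date rule alone would exclude it, but the overlap and continuation sentences settle it as Prior, Concomitant and Post, which the fix also gives.
- *A late-started ongoing drug is misfiled.* It gets a surplus Concomitant label, but it is also Post under either reading.
- *The end date is the wrong test altogether.* It is the right test for the lower bound; only the upper bound is misplaced.
- *Early EUT stoppers create a long stretch of affected records.* That would require them to be followed to a visit timed from Week 16. Section 8.1 counts stopping treatment in EUT separately from leaving EUT, but the SAP does not say how long such participants are followed.
- *The AE or PVR results are at risk.* Neither Section 9.2.1 nor Section 10.2 uses the medication class.

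**Conclusion.** The rule is wrong as written, and the consequence is minor. Under either reading of the continuation sentence, a drug started on treatment and stopped on or after D fails the working rule for Concomitant, against the section's own lead definition. An ongoing drug started on or after D passes it. A complete end date on D and a partial one that could be D are treated differently.

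The effect is confined to class labels for records with dates at or beyond D. On the planned visit schedule these should be few, assuming that medication dates are collected up to the follow-up visits and not beyond. With one treated participant and listings only, a reader shown the start and stop dates can correct the class by eye. Whether that participant has any affected record cannot be told from the SAP.

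**What to change.** Reword Section 8.4.1, with D as the date 30 days after the last dose:

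- **Concomitant:** start date before D (or recorded as started prior to study drug), and end date on or after first dose or ongoing. Both conditions apply to ongoing drugs, so being ongoing no longer qualifies a drug by itself.
- **Partial or missing dates:** Concomitant if the possible dates are compatible with both conditions, in place of the present rule, which looks only at the end date.
- **Post:** any use on or after D, whatever the start date. The continuation sentence is then redundant and can go. State whether a drug ongoing at a last contact before D counts as Post.

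The Prior rule and the overlap sentence can stay. With these rules every pattern in the table has a class, and each class agrees with the section's lead definitions. The cost is a few lines of SAP text and one derivation, with no new data.

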8.4.2. Medical and Surgical Treatment Procedures

All medical and surgical treatment procedures will be coded using MedDRA, Version 25.0. All medical and surgical treatment procedures will be presented in a by-participant listing.

8.5. COVID-19 Impact

Potential COVID-19 impact is captured in the eCRF and will be summarized and listed as part of respective summaries or by-participant listings.

Disposition summary and listing will include:

- Screen failure related to COVID-19;
- Early termination of study related to COVID-19.

AE overview table and listings will include:

• AEs that fall into the category of COVID-19 related.

Listing of protocol deviations will include:

• Protocol deviations due to COVID-19.

9. SAFETY AND EFFICACY

9.1. Primary Endpoint

The analysis of primary endpoint in terms of frequency of TEAEs will be described in Sections 10.2 to 10.3 of this SAP.

9.2. Secondary Endpoints

9.2.1. Evaluation of Change in Pulmonary Vascular Resistance

PVR and the change from baseline in PVR at 8 and 24 hours after TPIP administration in single-dose inpatient treatment period will be summarized by dose group (if applicable) for the PD population. All measurements of PVR will be included in a byparticipant listing.

9.2.2. Evaluation of Pharmacokinetics of Treprostinil

The analysis of TRE plasma PK parameter of C_{max} , t_{max} , AUC_{t1-t2} , AUC_{0-inf} , $t_{1/2}$ will be described in Section 11.

9.3. Exploratory Objectives

9.3.1. Evaluation of Pharmacodynamics

PD assessments of PAP, RVP, RAP, CO, oxygen consumption, MVO₂, SpO₂, (from right heart catheter (RHC)), heart rate, systemic blood pressure, hemoglobin, pulmonary capillary wedge pressure (PCWP), cardiac index (CI) and changes from baseline at 8 and 24 hours after TPIP administration in single-dose inpatient treatment period will be summarized by dose group (if applicable) for the PD population. In a by-participant listing all observed time points together with their changes at 8 and 24 hours after TPIP administration will be listed.

Individual profiles using planned sampling times will be provided for PD assessments (all participant profiles of one parameter will be shown in one plot, [spaghetti plot]).

